## **3.0 OBJECTIVES AND ENDPOINTS**

## 3.1 Objectives

### Efficacy

- Primary: To assess the proportion of responders to treatment with ensifentrine based on the improvement in individual CAT scores when added to standard of care in symptomatic subjects with moderate to severe COPD in routine clinical practice.
- Secondary: To investigate the effects of ensifentrine on COPD symptoms, as measured by the CAT in symptomatic subjects with moderate to severe COPD when added to standard of care in routine clinical practice.

### Safety

• Safety of ensifentrine.

## 3.2 Endpoints

### Efficacy

- Primary: The proportion of CAT score responders, defined as an improvement from baseline of ≥2 at Week 12.
- Secondary:
  - The proportion of CAT score responders, defined as an improvement from baseline of ≥2, at Week 6.
  - CAT score at Week 6 and Week 12 (change from baseline).
  - CAT score at Week 6 and Week 12 (item-level change from baseline).

### Safety

- Incidence and proportion of AEs.
- Change from baseline in vital signs (blood pressure and pulse rate).

# 4.0 STUDY DESIGN

## 4.1 Overall Design

This is a Phase IIIb, single-center, open-label study investigating the effect of treatment with twice daily nebulized ensifentrine (3 mg) over 12 weeks on CAT scores in subjects with moderate to severe COPD when added to standard of care in routine clinical practice. The CAT is a validated, short, and simple patient completed questionnaire which has been developed for use in routine clinical practice to measure the health status of patients with COPD.

At Visit 1, potential subjects will be provided with the informed consent for participation in the study. Following signature on the informed consent, the following information will be collected, and procedures performed to confirm subject eligibility for participation in the study in the following sequence:

- CAT Training followed by subject completion of the CAT on paper
- Modified Medical Research Council Dyspnea Scale (mMRC)
- Collect and record demographic data
- Eligibility review (inclusion and exclusion criteria)
- Review and record medical, surgical, COPD and smoking history
- Review of prior and concomitant medication (refer to Table 5 for Prohibited Medications)

At Visit 2, subject eligibility will be confirmed (screening tests will be verified, and it will be assured that the subject meets all inclusion criteria and no exclusion criteria). Spirometry will be performed, a physical examination completed, and vital signs will be assessed. Eligible subjects will receive a nebulizer and compressor and will be administered their first dose of ensifentrine (3 mg) in-clinic during training on nebulizer use. Adverse events will be assessed. Subjects will receive a 6-week supply of ensifentrine (3 mg) to be administered twice-daily (BID) with a standard jet nebulizer. Ensifentrine will be administered BID for a total of 12 weeks.

At Visit 3 (Week 6), subjects will return and complete the CAT first, their concomitant medication will be reviewed, their vital signs and safety will be assessed. Subjects will receive a 6-week supply of ensifentrine (3 mg) administered BID.

At Visit 4 (Week 12), subjects will complete the CAT first, their concomitant medication will be reviewed, their vital signs and safety will be assessed. After 12 weeks, treatment with nebulized ensifentrine (3 mg) will end.

The CAT will be completed on paper at Visits 1, 3 and 4 prior to any study procedures to avoid influencing the subject's response. All questions must be answered. Answers to each question will be logged into the eCRF by the study team.

A follow-up phone call will be made to the subject approximately one week after the end of treatment.

Subjects may remain on prescribed short- and long-acting COPD medications throughout participation provided they are not included in the prohibited medication list. COPD exacerbations should be treated at physician's discretion as per usual practice.

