### **Treatment Groups and Duration**

All subjects meeting eligibility criteria and consenting to participation in the study will receive nebulized ensifeatrine (3 mg) BID with a standard jet nebulizer for 12 weeks.

Total duration of subject participation is approximately 14 weeks.

Recruitment is anticipated to take 3 months.

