## 5.1 Inclusion Criteria

- 1. Capable of giving informed consent indicating that they understand the purpose of the study and study procedures and agree to comply with the requirements and restrictions listed in the ICF and in this protocol.
- 2. Aged 40 to 80 years of age inclusive, at the time of screening.
- 3. Sex:
  - Males are eligible to participate if they agree to use contraception as described in the contraceptive guidance (Appendix 4) from screening and throughout the study and for at least 30 days after the last dose of study medication.
  - Females are eligible to participate if they are not pregnant, not breastfeeding, and  $\geq 1$  of the following conditions apply:
    - a) Not a woman of childbearing potential (WOCBP) as defined in Appendix 4.
      - OR
    - b) A WOCBP who agrees to follow the contraceptive guidance in Appendix 4 from screening and throughout the study and for at least 30 days after the last dose of study medication.
- 4. Current or former cigarette smoker with a history of cigarette smoking ≥ 10 pack years. Note: Pipe and/or cigar use cannot be used to calculate pack-year history. Former smokers are defined as those who have stopped smoking at least 6 months prior to screening. Smoking cessation programs are permitted during the study.
- An established clinical history of COPD as defined by the American Thoracic Society (ATS)/European Respiratory Society (ERS) guidelines with symptoms compatible with COPD.
- 6. Pre- and post-bronchodilator (4 puffs of albuterol) spirometry at Visit 2 demonstrating the following:
  - Pre- and post-albuterol  $FEV_1$ /forced vital capacity (FVC) ratio of < 0.70.
  - Post-albuterol  $FEV_1 \ge 30$  % and  $\le 75$ % of predicted normal.
- 7. A score of  $\geq 2$  on the modified Medical Research Council Dyspnea Scale at Visit 1.
- 8. A score of  $\geq 10$  on the COPD Assessment TestTM at Visit 1.
- 9. Demonstrates stable use of dual (LAMA+LABA) or triple (LAMA+LABA+ICS) maintenance therapy, in any form (except nebulized) for at least 8 weeks prior to screening and agrees to continue use for the duration of the study. *Note: The*

number taking LAMA+LABA+ICS will be capped at ten (10). The use of LAMA or LABA alone or with ICS is not permitted (e.g., LABA+ICS, LAMA).

- 10. Capable of withholding short-acting rescue medications for 4 hours, Twice-Daily maintenance therapy for 24 hours or Once-Daily maintenance therapy for 48 hours prior to Visit 2.

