## 5.3 Rescreening

Subjects who are screen failures (Section 5.4) may be rescreened with approval from the Medical Monitor. Rescreened subjects should be assigned a new subject number different from the initial screening event.

Rescreening due to failure to meet the following Inclusion Criteria is not allowed for Inclusion Criteria # 5, 6, 7, or 8.

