### 8.4.5 **Primary Efficacy Endpoint**

### 8.4.5.1 Primary Efficacy Hypothesis

The primary efficacy endpoint for this study is the proportion of CAT responders, defined as an improvement from baseline  $\geq 2$ , at Week 12. This will be evaluated for the null hypothesis that the proportion is not different than 0:

H0: 
$$p = 0$$
 vs. H1:  $p > 0$ 

Where p is the proportion of subjects at Week 12 with an improvement from baseline of at least 2 in CAT total score. A two-sided unadjusted 95% confidence interval for the proportion will be used to determine study success with the lower bound of the CI > 0 indicating success.

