### 8.4.6.2 Change from Baseline CAT Individual Item Analyses

The CAT questionnaire contains 8 individual items with scores ranging from 0-5. Each individual item will be summarized at Week 6 and Week 12 in the same manner as the change from baseline CAT Total Score secondary efficacy endpoint. The baseline for individual items is the item score at the baseline assessment. Least square mean estimates, standard errors, and corresponding 95% confidence limits will be presented at each post-treatment time of assessment

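### The single Visit 1 CAT serves as entry test and, by inference, as baseline, so regression to the mean adds a modest bias toward benefit in this single-arm study

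*Protocol*

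**What the plan says.** - **Timing.** Protocol 4.1: "The CAT will be completed on paper at Visits 1, 3 and 4 prior to any study procedures". Protocol 8.2 and the schedule tables in both documents agree. No CAT is scheduled at Visit 2, when the first dose is given.
- **Entry.** Inclusion criterion 8 requires a score of at least 10 "on the COPD Assessment Test TM at Visit 1". Protocol 5.3 bars a second attempt: "Rescreening due to failure to meet the following Inclusion Criteria is not allowed for Inclusion Criteria # 5, 6, 7, or 8". One score decides entry.
- **Endpoint.** Protocol 3.2, primary: "The proportion of CAT score responders, defined as an improvement from baseline of ≥2 at Week 12". Change in total score and item scores is secondary.
- **Baseline.** No visit is named. The nearest to a definition is SAP 8.4.6.2: "The baseline for individual items is the item score at the baseline assessment". Protocol 8.0 lets routine pre-consent procedures serve as baseline if they fall within the scheduled time frame, but provides no separate baseline CAT.
- **Control.** None. The synopsis says: "All subjects meeting eligibility criteria and consenting to participation in the study will receive nebulized" ensifentrine.
- **Model.** SAP 8.4.5.2 and 8.4.6.1 include baseline CAT total score as a covariate.

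Neither document mentions regression to the mean, a repeat baseline, a run-in or an external reference rate.

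**The concern.** A CAT score is a true level plus day-to-day error. Admitting subjects on an observed score of at least 10 favours those whose error at Visit 1 was upward and keeps out those whose error was downward. When the error is redrawn at Weeks 6 and 12, the expected score falls although nothing has changed. This is a shift in the mean, distinct from symmetric scatter around zero.

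A control arm would carry the same shift and cancel it. Here there is none. The covariate does not help: in a single arm, a least-squares mean taken at the average observed baseline equals the average change, regression included.

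Protocol 9.1 says the study exists to quantify CAT improvement and responder proportions. A bias in one direction in those estimates matters for that purpose even where no decision turns on it.

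**Working it through.** **1. The plan's own figures (Protocol 9.2, SAP 5).** Count interval: 6 ± 1.96 × √6 = (1.199, 10.801), as stated. Upper limit for mean change: −1 + 1.96 × 4.5/√20 = 0.97, or 1.11 with t on 19 df. Both are below +2, as stated.

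**2. Inputs.** From the documents: threshold 10, change SD 4.5, n = 20, responder = improvement of at least 2. Assumed, because the documents give none: unselected CAT mean of 12 to 22 and SD of 6 to 8 in the pool being screened.

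**3. Formula.** If the true score is unchanged and errors are independent, the change SD is √2 × error SD. The error SD is then 4.5/√2 = 3.18 and the error variance 10.125. Reliability is 1 − 10.125/SD². With z = (10 − mean)/SD,

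spurious improvement = (1 − reliability) × SD × φ(z)/(1 − Φ(z)) = (10.125/SD) × φ(z)/(1 − Φ(z)).

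Example, mean 18 and SD 6: z = −1.333; φ = 0.1640; 1 − Φ = 0.9088; (10.125/6) × 0.1640/0.9088 = 0.30 units.

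| Assumed source mean | SD 6 | SD 7 | SD 8 |
|---|---|---|---|
| 15 | 0.60 | 0.59 | 0.57 |
| 18 | 0.30 | 0.34 | 0.36 |
| 22 | 0.09 | 0.14 | 0.18 |

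**4. Responder share with no true effect.** Scatter alone: Φ(−2/4.5) = 32.8% on a continuous scale, or Φ(−1.5/4.5) = 36.9% for integer scores. Adding selection, by simulation (integer scores 0 to 40, unchanged true score, at least 2 million subjects per setting, SD 6):

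| Assumed source mean | Mean change from Visit 1 | Responders from Visit 1 | Responders from a separate baseline |
|---|---|---|---|
| 12 | −0.94 | about 45% | about 37% |
| 15 | −0.55 | about 41% | about 37% |
| 18 | −0.27 | about 39% | about 37% |
| 22 | −0.08 | about 37.5% | about 37% |

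These mean changes are slightly smaller than in step 3 because an integer score of at least 10 corresponds to a cut at 9.5. With 9.5 in the formula, mean 12 and SD 6 give 0.93. With a separate baseline and independent errors, the mean change returns to 0.00.

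**5. Effect on the success decision (SAP 8.4.5.1: lower limit above 0).** By the count-based interval of SAP 5, 3 − 1.96√3 = −0.39 fails and 4 − 1.96√4 = 0.08 succeeds, so 4 of 20 suffices. With no drug effect, the chance of at least 4 responders is 97% at a 36.9% share (bias removed). It is 97% to over 99% at shares of 37.5% to 45% (bias present).

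**6. Effect on the mean-change aim.** If 0.36 of the planned 1 unit were regression, the upper limit would be −0.64 + 1.97 = 1.33, or 1.47 with t. Both are still below +2.

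**7. Could 20 subjects measure the shift?** The standard error of a Visit 1-to-baseline mean change is 4.5/√20 = 1.01. The 95% interval is about ±2 units, around a shift of a few tenths.

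**The case against.** The strongest reply is that the bias is small and changes nothing the plan decides. On the decision, that stands (steps 5 and 6). On size, it largely stands. Entry also requires mMRC of at least 2, post-albuterol FEV1 of 30% to 75% predicted and stable dual or triple maintenance therapy, so a pool averaging close to 10 is hard to defend. The bias shrinks as the mean rises. Excluding recent hospitalization, systemic steroids and lower respiratory infection limits transiently high scores, and barring rescreening stops repeated attempts to qualify. None of this removes selection on one error-prone score.

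A reader might infer that regression could explain the whole planned 1-unit improvement. Varying SD and reliability freely gives up to 0.69 units at mean 18 and 1.07 at mean 15. That corner (SD 8, reliability 0.7) implies a change SD of 8 × √(2 × 0.3) = 6.2, which conflicts with the plan's 4.5. At 4.5, only a source mean near 12 brings the shift close to 1 unit, and nothing in the documents supports such a mean.

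A second baseline also has limits. Visit 2 falls within 7 days of Visit 1, so correlated errors would leave some regression in place. Home completion differs from the clinic completion that Protocol 8.2 sets for follow-up. Both objections stand and belong in the write-up.

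**Conclusion.** The point holds as a modest, one-directional bias. With no true effect and a change SD of 4.5, the spurious mean improvement is about 0.6, 0.3 to 0.4 and 0.1 to 0.2 units at assumed source means of 15, 18 and 22. Selection adds roughly 1 to 8 percentage points to a responder share that scatter alone puts near 37%; the upper end needs a source mean near 12. The size rests on the assumed source distribution and on independent errors. That Visit 1 is the baseline is inferred from the schedule, though no other scheduled CAT could serve.

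A reader might also infer that this bias is what makes the success claim unsafe. The calculations do not support that: scatter alone already gives a 97% chance of success with no drug effect. The comparison with zero is the larger, separate problem, and a new baseline does not solve it.

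Rating: a cheap improvement.

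**What to change.** - Use the Visit 1 CAT for eligibility only.
- Add one further paper CAT between Visit 1 and the first dose, completed before the pre-spirometry withholding of maintenance therapy begins, so that it reflects usual therapy. Site staff check it for completeness, and no threshold applies to it.
- Name that score as baseline in SAP 8.4.5 and 8.4.6. The baseline visit needs naming in any case.
- Use the Visit 1 score as baseline only in a sensitivity analysis. Do not substitute it for missing forms in the primary analysis, which would mix two baselines among about 20 subjects.
- Report the Visit 1-to-baseline change descriptively with its confidence interval (about ±2 units at n = 20), not as a measurement of the regression effect.

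**Cost.** One one-page form per subject and a few sentences in the protocol and SAP. Downsides to state: completion at home rather than in clinic; a few missed forms, each removing a subject from the Full Analysis Set because it requires a baseline CAT and nothing is imputed; a Visit 2 date that leaves room before the 24- or 48-hour hold; and residual regression if errors are correlated over the interval of up to 7 days.

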## 4.2 Justification for Dose

A 3 mg twice daily dose was selected as the phase III dose for the COPD clinical trials based on data from two 4-week Phase IIb studies RPL554-CO-203 and RPL554-CO-205 which showed clinically meaningful and statistically significant improvements in pulmonary function with the 3 mg dose over the 12-hour dosing interval, in subjects with or without additional bronchodilator background therapy. Two Phase III studies, RPL554-CO-301 and RPL554-CO-302 confirmed the efficacy and safety of 3 mg ensifentrine BID in subjects with COPD. Ensifentrine 3 mg twice daily (OHTUVAYRE) is the approved dose and regimen for the maintenance treatment of COPD in adult patients (OHTUVAYRE Prescribing Information).

## 4.3 End of Study Definition

A subject is considered to have completed the study if he/she has successfully completed all scheduled visits and completed follow-up contact. With no rescheduled visits, the study should last approximately 14 weeks.

The end of the study is defined as the date of the last follow-up contact of the last subject in the study.

# 5.0 STUDY POPULATION

Prospective approvals of protocol deviations to recruitment and enrollment criteria, also known as protocol waivers or exemptions, are not permitted.

## 5.1 Inclusion Criteria

- 1. Capable of giving informed consent indicating that they understand the purpose of the study and study procedures and agree to comply with the requirements and restrictions listed in the ICF and in this protocol.
- 2. Aged 40 to 80 years of age inclusive, at the time of screening.
- 3. Sex:
  - Males are eligible to participate if they agree to use contraception as described in the contraceptive guidance (Appendix 4) from screening and throughout the study and for at least 30 days after the last dose of study medication.
  - Females are eligible to participate if they are not pregnant, not breastfeeding, and  $\geq 1$  of the following conditions apply:
    - a) Not a woman of childbearing potential (WOCBP) as defined in Appendix 4.
      - OR
    - b) A WOCBP who agrees to follow the contraceptive guidance in Appendix 4 from screening and throughout the study and for at least 30 days after the last dose of study medication.
- 4. Current or former cigarette smoker with a history of cigarette smoking ≥ 10 pack years. Note: Pipe and/or cigar use cannot be used to calculate pack-year history. Former smokers are defined as those who have stopped smoking at least 6 months prior to screening. Smoking cessation programs are permitted during the study.
- An established clinical history of COPD as defined by the American Thoracic Society (ATS)/European Respiratory Society (ERS) guidelines with symptoms compatible with COPD.
- 6. Pre- and post-bronchodilator (4 puffs of albuterol) spirometry at Visit 2 demonstrating the following:
  - Pre- and post-albuterol  $FEV_1$ /forced vital capacity (FVC) ratio of < 0.70.
  - Post-albuterol  $FEV_1 \ge 30$  % and  $\le 75$ % of predicted normal.
- 7. A score of  $\geq 2$  on the modified Medical Research Council Dyspnea Scale at Visit 1.
- 8. A score of  $\geq 10$  on the COPD Assessment TestTM at Visit 1.
- 9. Demonstrates stable use of dual (LAMA+LABA) or triple (LAMA+LABA+ICS) maintenance therapy, in any form (except nebulized) for at least 8 weeks prior to screening and agrees to continue use for the duration of the study. *Note: The*

number taking LAMA+LABA+ICS will be capped at ten (10). The use of LAMA or LABA alone or with ICS is not permitted (e.g., LABA+ICS, LAMA).

- 10. Capable of withholding short-acting rescue medications for 4 hours, Twice-Daily maintenance therapy for 24 hours or Once-Daily maintenance therapy for 48 hours prior to Visit 2.
- 11. Capable of using the study nebulizer correctly.
- 12. Ability to perform acceptable spirometry in accordance with ATS/ERS guidelines.
- 13. Willing and able to attend all study visits and adhere to all study assessments and procedures.

## 5.2 Exclusion Criteria

- 1. Hospitalizations for COPD (or COPD exacerbation), pneumonia, or other serious infection or treatment with oral or parenteral (oral, intravenous, or intramuscular) glucocorticoids within the past 12 weeks.
- 2. Lower respiratory tract infection within the past 6 weeks or an active infection at screening.
- 3. History of life-threatening COPD, including Intensive Care Unit admission and/or requiring intubation within 1-year of screening.
- 4. Major surgery (requiring general anesthesia) within the past 6 weeks, lack of full recovery from surgery at screening, or planned surgery through the end of the study.
- 5. Concomitant clinically significant pulmonary disease other than COPD (e.g., asthma, tuberculosis, lung cancer, bronchiectasis, sarcoidosis, lung fibrosis, interstitial lung diseases, sleep apnea (unless controlled with stable continuous positive airway pressure [CPAP] use), known alpha-1 antitrypsin deficiency, core pulmonale or other non-specific pulmonary disease).
- 6. Severe comorbidities including unstable cardiac, (e.g., myocardial infarction within 1 year prior to screening, unstable angina within 6 months prior to screening, or unstable or life-threatening arrhythmia requiring intervention within 3 months prior to screening) or any other clinically significant medical conditions including uncontrolled diseases (e.g., endocrine, neurological, hepatic, gastrointestinal, renal, hematological, urological, immunological, psychiatric or ophthalmic diseases) that would, in the opinion of the Investigator, preclude the subject from safely completing the required tests or the study, or is likely to result in disease progression that would require withdrawal of the subject.
- 7. HIV infection or other immunodeficiency.
- 8. Previous lung resection or lung reduction surgery within 1-year.
- Long term oxygen use defined as oxygen therapy prescribed for greater than 12 hours per day. Note: As needed oxygen use (≤ 12 hours per day) is not exclusionary.

- 10. Pulmonary rehabilitation unless such treatment has been stable from 4 weeks prior to screening and remains stable during the study. *Note: Pulmonary rehabilitation programs should not be started or completed during participation in the study.*
- 11. History of or current malignancy of any organ system, treated or untreated within the past 5 years, except for localized basal or squamous cell carcinoma of the skin.
- 12. Significant psychiatric disease that would likely result in the subject not being able to complete the study, in the opinion of the Investigator.
- 13. Findings on physical examination that an investigator considers to be clinically significant.
- 14. Known alanine aminotransferase (ALT)  $\ge 2 \times$  upper limit of normal (ULN), alkaline phosphatase and/or bilirubin  $> 1.5 \times$  ULN (isolated bilirubin  $> 1.5 \times$  ULN is acceptable if fractionated bilirubin < 35%).
- 15. Known diagnosis of severe chronic kidney disease.
- 16. Any other known abnormal clinical, cardiac or laboratory (hematology, biochemistry or viral) findings, deemed by an investigator to be clinically significant. *Note: Clinically significant abnormal chemistry and/or hematology may be repeated during the screening process.*
- 17. Use of prohibited medications within the time intervals defined in Section 6.7.2.
- 18. Current or history of drug or alcohol abuse within the past 5 years.
- 19. Women who are breast feeding.
- 20. Use of an experimental drug within 30 days or 5 half-lives of screening, whichever is longer, and/or participation in a study treatment-free follow-up phase of a clinical study within 30 days prior to screening.
- 21. Use of an experimental medical device or participation in a follow-up phase of an experimental medical device clinical study within 30 days prior to screening.
- 22. Affiliation with the investigator site, including an Investigator, Sub-Investigator, study coordinator, study nurse, other employee of participating investigator or study site or a family member of the aforementioned.
- 23. A disclosed history or one known to the Investigator of significant noncompliance in previous investigational studies or with prescribed medications.
- 24. Any other reason that the Investigator considers makes the subject unsuitable to participate.

